Duration of Study Participation	Participants will be followed during index ED visit/hospitalization. There will be a phone call at 48-72 hours for those discharged within 24 hours. All participants will receive a follow up phone call at 28 days post emergency room discharge.
Number of Subjects	1,000 subjects will be enrolled, with 500 each in the standard of care and interventional arms.
Number of Sites	9
Statistical Considerations	The primary aim of the study is to compare the two study arms in terms of a difference in mean length of hospital stay (LOS) between the two arms. We have conducted a power evaluation using the estimated mean and standard deviation based on observed data from ROMICAT I and simulated data based on health outcomes. We will have 95% power to detect a difference in 10 hours of LOS at a Type-1 error rate of 5% for an independent samples t-test using 500 patients in each arm.

Part I: Study Overview

The study is designed as a randomized, controlled, diagnostic, multicenter trial and will enroll 1,000 participants at nine sites over a 15 month period. Participants presenting with acute chest pain in the ED will be randomized to a standard of care arm (SOC) or interventional arm; patients in the interventional arm will receive standard evaluation supplemented by contrast-enhanced cardiac computed tomography (CT) imaging (Figure 1).

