In both arms, the initial Emergency Department (ED) evaluation (electrocardiogram [ECG], physical examination, clinical presentation, renal function lab, and medical history) will determine eligibility of patients. After randomization, standard of care will be performed in both arms. However, for patients randomized to the interventional arm, a CT will be performed. The following decisions made by the caregiver team will be tracked: admission or discharge after initial ED evaluation plus CT/other initial diagnostic test, in admitted participants, the length of hospital stay, the extent of further testing including serial cardiac markers and ECG, and other diagnostic tests or interventions. For safety reasons, participants discharged in less than 24 hours of ED arrival will receive a phone call 48-72 hours after discharge. All participants will receive a 28-day follow-up phone interview. The efficiency of each strategy will be determined by comparing 1) the length of hospital stay (primary endpoint), 2) the time to diagnosis (secondary endpoint), 3) the rates of ED discharge (secondary endpoint), 4) utilization of other diagnostic testing, i.e. invasive coronary angiograms, and resulting interventions, i.e. coronary revascularization procedures during index hospitalization and 28 days (secondary endpoint). The safety of the two strategies will be compared by determining the occurrence of adverse events within 48-72 hours in directly discharged patients as well as determination of major adverse cardiovascular events (MACE) within 28 days after discharge from the index hospitalization. We will also perform a cost and cost effectiveness analysis. In subsequent analyses, we will determine the patient, physician, and institutional factors that affect the primary endpoint or secondary endpoints.

Primary Objective:

To determine whether length of hospital stay is significantly shortened in the interventional arm vs. SOC.

Hypothesis:

Adding cardiac CT to the initial ED evaluation of subjects with acute chest pain decreases length of hospital stay.

Part II: Study Description

1. Background and Significance

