28 Days: Defined as 28 days post the day of discharge from index hospitalization.

Hypothesis: *The rates of MACE in both arms during the 28 day follow up period will be similar.*

6. To estimate and compare the sensitivity, specificity, NPV and PPV of contrast-enhanced CT and non-contrast CT, with clinical diagnosis of ACS as the reference standard.

Hypothesis: *The test characteristics of contrast enhanced CT will be significantly better than those of a non-contrast CT for the diagnosis of ACS.*

7. Determine whether cost of care (per TSI) for index hospitalization and after 28 days is decreased by implementing cardiac CT into the early ED evaluation of patients with acute chest pain.

Hypothesis: *Incorporation of cardiac CT into standard ED evaluation of patients with acute chest pain will decrease the cost of care.*

8. Determine the cost-effectiveness of incorporating cardiac CT into the standard ED evaluation of patients with acute chest pain over a 28-day and lifetime horizon as compared to SOC.

Hypothesis: *Incorporating cardiac CT into the standard evaluation of patients with acute chest pain will be cost-saving and cost-effective over a 28-day and lifetime horizon.*

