of discharge rates we will have a 100% chance at a significance level of 0.05 to detect a 17% increase in discharge rates from 15% to 32%.

The comparison of time to discharge among patients who are admitted to the hospital is complicated by the fact that the two groups will not be the same group of patients. For instance, patients who would have been discharged in the cardiac CT group but admitted in the usual care group may have a relatively shorter time post admission than patients who would have been admitted in both groups. We have developed methods for analyzing these types of data using causal inference that will be applied to this analysis.⁶¹ A similar analysis will be applied to other subgroups such as those with and without ACS.

To compare the two study arms in terms of cardiac health care utilization during the index visit. Health care utilization components will include invasive coronary angiograms and coronary revascularization..

The analysis for this secondary aim will be performed from the intent to treat perspective. Health care utilization will be assessed using medical record review. Measures of key components of utilization will be compared across the two study groups using procedures appropriate for each measure (rate or count).

In particular the two arms will be compared in terms of the number of invasive coronary angiograms. This secondary endpoint will be analyzed in terms of a non-inferiority trial. In a non-inferiority trial the null hypothesis is that cardiac CT is worse than usual care in that the rate of coronary angiograms is increased and the alternative hypothesis is that it is not in worse and the rate of angiograms is the same. The reason for reversing the usual null and alternative hypothesis is that the purpose of this analysis is to prove that cardiac CT is not worse than usual care, this would not be accomplished by just showing that the difference between the two was not significant.

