This analysis will be performed from the intent to treat perspective. CP and CT related health care utilization will be assessed using medical record review. Measures of key components of utilization will be compared across the two study groups using procedures appropriate for each measure (rate or count).

We expect that the rate of additional cardiac work-up will be 29% in the SOC arm and will be 14% in the interventional arm. We will have >95% power to detect this difference.

We expect that the rate of hospital admissions with additional diagnostic cardiac testing will be 9.3% in the SOC arm and will be 4% in the interventional arm. We will have >95% power to detect this difference.

We expect that the rates of these measures will be associated with the CT findings at index hospitalization.

To evaluate the cost and cost-effectiveness of incorporating cardiac CT into the standard ED evaluation of patients with acute chest pain

These analyses will be performed by the Decision Analysis and Cost-Effectiveness Center (DACE). Therefore, the sites will collect and provide the necessary data to the DACE and the costs will be derived from the cost-accounting database (TSI). As a first step, incorporating cardiac CT into the standard evaluation of patients with acute chest pain will be tested for cost-saving over a 28-day and lifetime span as compared to standard care. Further on, cost-effectiveness of incorporating cardiac CT into the standard ED evaluation of patients with acute chest pain will be determined using first-order Monte Carlo microsimulations.

To compare the two study arms in terms of rates of MACE (cardiac death, AMI, revascularization, unstable angina, and rehospitalization) within 28 days.

The analysis for this secondary aim will be performed from the intent to treat perspective. The occurrence of MACE will be assessed via patient follow-up and medical chart review. The primary analysis for this aim will be performed at the patient level by determining whether any MACE occurred or not. Event rates will be estimated and compared between study groups using exact procedures. In a secondary analysis, the rates of each type of MACE will be examined separately.

Sample Size- Safety Considerations- Missed ACS: Mistaken discharges are the primary safety issue in this study. All available data indicate that the absence of any detectable CAD (absence

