Appendix B: Adjudication of Events by Clinical Events Committee

Introduction

Because patient safety is one of the concerns in a trial assessing new technology, clinical events and serious adverse events will be independently adjudicated by the Clinical Events Committee, under the direction of [name]. This committee will adjudicate events in all subjects who potentially could have a major adverse cardiovascular event (MACE), such as, death, unstable angina pectoris (UA), myocardial infarction (MI), or coronary revascularization that occur after symptom assessment at patient's initial emergency department (ED) presentation. There is a possibility that MACE will occur during index hospitalization. For example, a second episode of chest pain diagnosed as acute coronary syndrome (ACS) occurring after the chest pain the patient presented with has resolved and all diagnostic tests were negative or recurrence of symptoms with or without hospitalization and re-hospitalization with or without testing.

Definitions of Adverse Cardiovascular Events

Adverse cardiovascular events comprise cardiovascular death, MI, unstable angina pectoris (UAP), coronary revascularization and/or re-hospitalization that are distinct from the qualifying event (after patient's initial ED presentation).

Definitions of events are listed below:

Cardiovascular Death: Any sudden cardiac death, death due to acute myocardial infarction, death due to heart failure, death due to stroke, and death due to other cardiovascular causes. In addition, any death without a clear non-cardiovascular cause, or a death without known cause will be considered cardiovascular death.

MI: In Subjects with no recent revascularization in whom normal biomarkers were never elevated or have been documented to return to normal after a qualifying (or recent) MI who meet the following criteria:

- 1.) Typical cardiac biomarker rise and/or fall AND at least one of the following:
 - a) Ischemic discomfort at rest lasting ≥ 10 minutes
 - b) ECG changes indicative of ischemia (ST elevation ≥ 0.1 mV or ST depression ≥ 0.05 mV, or new T-wave inversions).

OR;

- 2.) Development of new, abnormal Q waves (≥ 30 msec in duration and ≥ 1 mm in depth) in >2 contiguous precordial leads or ≥ 2 adjacent limb leads; or increase R amplitude in V1-V3 consistent with posterior infarction.

OR;

- 3.) Pathologic findings of an acute MI

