- 4) Sudden unexpected cardiac death, including cardiac arrest, often with symptoms suggestive of myocardial ischemia, accompanied by presumably new ST elevation, or new LBBB, or evidence of fresh thrombus in a coronary artery by angiography and/or at autopsy, but death occurring before blood samples could be obtained, or at a time before the appearance of cardiac biomarkers in the blood

In subjects with percutaneous coronary intervention within 48 hours, an elevation of CK-MB >3x ULN distinct from a prior event will be considered to be a procedural MI.

In subjects with CABG within 48 hours, an elevation of CK-MB > 10x ULN distinct from a prior event will be considered to be a procedural MI.

UA: An event not meeting the definition of myocardial infarction and with the following characteristics. Chest pain or anginal equivalent at rest or in accelerating pattern AND at least one of the following objective signs:

- a) New ST-segment changes
- b) New TWI
- c) Positive stress test with imaging showing ischemia
- d) Positive stress test without imaging resulting in increased anginal medication
- e) Cath \geq 70% stenosis or thrombus

Urgent Coronary Revascularization: Ischemic discomfort or equivalent meeting the following criteria:

- a) Lasting \geq 10 minutes at rest, or repeated episodes at rest lasting \geq 5 minutes, considered to be myocardial ischemia upon final diagnosis

AND;

- b) Prompting coronary revascularization during an unscheduled visit to healthcare facility or during an unplanned (or prolonged) hospitalization for these symptoms.

Note: Attempted revascularization procedures, even if not successful will be counted. Potential ischemic events meeting the criteria for myocardial infarction will not be adjudicated as urgent coronary revascularization.

Re-hospitalization: Coronary ischemia requiring re-hospitalization is defined as an event not meeting the definitions of myocardial infarction or urgent coronary revascularization: ischemic discomfort or equivalent meeting the following criteria:

- a) Lasting \geq 10 minutes at rest, or repeated episodes at rest lasting \geq 5 minutes, or an accelerating pattern of ischemic discomfort (episodes that

are more frequent, severe, longer in duration and precipitated by minimal exertion), considered to be myocardial ischemia upon final diagnosis

AND;

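### The protocol expects similar 28-day MACE rates but sets no margin or confidence-limit criterion for showing it, and its MACE components and time window conflict between sections

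*Protocol*

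**What the plan says.** **Hypothesis and use.** Aim 5 in Protocol Section 3.2 states: "The rates of MACE in both arms during the 28 day follow up period will be similar". The Study Synopsis repeats this under its secondary hypotheses. Part I (Study Overview) compares the safety of the two strategies partly through "determination of major adverse cardiovascular events (MACE) within 28 days after discharge from the index hospitalization".

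**Analysis.** Section 7.2 analyses MACE by intention to treat, as any event versus none per patient: "Event rates will be estimated and compared between study groups using exact procedures". The paragraph gives no margin, alpha, expected rate or power.

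**Neighbouring endpoints.** For invasive angiograms, Section 7.2 adopts non-inferiority because the purpose is to show that CT is not worse, and "this would not be accomplished by just showing that the difference between the two was not significant". It sets a 5-point margin at one-sided 0.05 for angiograms and a 3.5-point difference for revascularization.

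**Definition and window.** Sections 3.2 and 7.2 list cardiac death, AMI, revascularization, unstable angina and rehospitalization. In Section 3.2 the 28 days are "Defined as 28 days post the day of discharge from index hospitalization". Appendix B uses cardiovascular death, gives criteria for revascularization only when urgent, and adjudicates events during the index stay as well as within 28 days.

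**The concern.** The MACE hypothesis has the same form as the angiogram hypothesis: CT should not make things worse. The protocol says why a plain difference comparison cannot establish that, then applies the reasoning to two utilization endpoints and not to the safety endpoint. If Aim 5 ends in a non-significant p-value, the protocol gives no basis for saying whether the hypothesis was supported.

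The size of the problem depends on how many events are counted, and the text leaves that open. Elective revascularizations prompted by CT, deaths from stroke or unknown cause, and events before discharge are in or out depending on which section is followed. Counting from discharge adds a further difficulty. Discharge occurs after randomization and is what the intervention is meant to bring forward, so it would help decide which early events count.

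**Working it through.** **Inputs.** There are 500 patients per arm (Study Synopsis: "1,000 subjects will be enrolled, with 500 each in the standard of care and interventional arms"). Section 7.2 supplies the angiogram rate of 10% with a 5-point margin at one-sided 0.05, and the revascularization rate of 5% (18/368) with 3.5 points. It gives no 28-day MACE rate, so rates of 1% to 5% are assumed.

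**Step 1: reproduce the protocol's own non-inferiority figures.** With equal true rates p, SE = √(2p(1−p)/500) and power = Φ(margin/SE − 1.645).
- Angiograms: SE = √(2 × 0.10 × 0.90/500) = 0.01897. Then 0.05/0.01897 − 1.645 = 0.990, giving 83.9% (stated: 84%).
- Revascularization: SE = √(2 × 0.05 × 0.95/500) = 0.01378. Then 0.035/0.01378 − 1.645 = 0.894, giving 81.4% (stated: 80%). A restricted-likelihood variance gives 79.4%.

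Both agree with the protocol, so its non-inferiority framework is clear and can be carried over to MACE.

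**Step 2: what a difference test can see.** Power of the two-sided Fisher test at 0.05, by full enumeration with 500 per arm:

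| Control rate (assumed) | CT rate | Power |
|---|---|---|
| 1% | 2% | 18% |
| 2% | 4% | 40% |
| 3% | 6% | 58% |
| 5% | 10% | 83% |

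Observed counts of 5 versus 14 (p = 0.061) or 10 versus 21 (p = 0.066) would still be non-significant.

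**Step 3: what 500 per arm can exclude.** The smallest margin with 80% power under equal true rates is (z₁₋α + 0.842) × SE, with z = 1.645 at one-sided 0.05 and 1.960 at one-sided 0.025.

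| Rate (assumed) | SE (points) | One-sided 0.05 | One-sided 0.025 |
|---|---|---|---|
| 1% | 0.629 | 1.6 | 1.8 |
| 2% | 0.885 | 2.2 | 2.5 |
| 5% | 1.378 | 3.4 | 3.9 |

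These are normal approximations. At 1% only about 5 events per arm are expected, so that row is rough.

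**Step 4: the endpoint text, side by side.**
- *Death:* Sections 3.2 and 7.2 say cardiac death. Appendix B says cardiovascular death, including "death due to stroke, and death due to other cardiovascular causes", and adds deaths without a known cause.
- *Revascularization:* it is unqualified in Sections 3.2 and 7.2 and in Appendix B's introductory and component lists. The only criteria stand under "Urgent Coronary Revascularization: Ischemic discomfort or equivalent meeting the following criteria".
- *A further meaning:* the missed-ACS paragraph in Section 7.2, repeated in Section 11, equates MACE with ACS within 30 days of direct ED discharge.
- *Window:* Section 3.2 starts at discharge from the index hospitalization. Appendix B recognises that MACE can occur during the index stay and adjudicates both periods, without saying whether index-stay events enter Aim 5.

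The last item matters for size. Revascularization is expected in about 5% of patients, so counting index-stay procedures could move the MACE rate from the first rows of Steps 2 and 3 to the last.

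**The case against.** Section 7.2 says rates will be estimated as well as compared, and exact procedures can include an exact confidence interval. The statistical analysis plan is not shown and may set a margin. This stands, and it is why the point is about a missing criterion and not about a test that cannot be rescued. It does not explain why the protocol states margins for two utilization endpoints but not for this one, and an analysis plan does not by itself remove contradictions in the protocol's own definitions.

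A reader might infer that a non-significant result would be taken as proof of safety. The protocol contains no such decision rule. It calls mistaken discharges the primary safety issue, gives them their own power statements, and also uses the 48-72 hour call. Those power statements concern a single group, though, and do not replace the between-arm comparison.

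A reader might also infer that early events are systematically misclassified because CT patients go home sooner. The documents do not show this. Appendix B adjudicates index-stay events in both arms, and no count of early events is given. The 28-day window itself moves little: the tabulated differences of 10.1 to 21.7 hours are 1.5% to 3.2% of 672 hours. Nor is Section 5.3 clearly a rival endpoint clock, since it times a telephone call. What remains is that the text does not say whether index-stay events count.

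Finally, all the MACE rates are assumed, and at 5% versus 10% the Fisher test has 83% power. The low-power figures therefore apply to low event rates, which is one more reason to settle the definition first.

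**Conclusion.** The point holds as a gap in the stated analysis and a contradiction in the endpoint. The hypothesis of similar 28-day MACE rates has no margin or confidence-limit criterion, contrary to the protocol's reasoning in the same section. At assumed rates of 1% to 3% with 500 per arm, a doubling would be detected with 18% to 58% power, so non-significance would not be evidence of similarity. The component lists and the treatment of index-stay events must be reconciled. The conflicts are read directly from the text. The power figures rest on the assumed rates, full enrolment and no loss to follow-up. This is a secondary endpoint, and the primary length-of-stay analysis is unaffected.

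**What to change.** 1. In Section 7.2, make the MACE risk difference with an exact or score confidence interval the analysis for Aim 5. Judge its upper limit against a margin the sponsor justifies, at one stated alpha. The angiogram analysis uses one-sided 0.05, whereas a two-sided 95% interval corresponds to one-sided 0.025, so the margin and the interval must use the same level. The Step 3 table shows what 500 per arm can support.
2. State that a non-significant p-value is not evidence of similarity.
3. Count MACE from randomization to one stated horizon, such as 28 days after discharge as now or a single fixed day. A fixed day has the advantage that the intervention cannot move it. Include index-stay events and also show them separately.
4. Reconcile Sections 3.2 and 7.2 (including the missed-ACS paragraph), Section 11 and Appendix B to one component list. Report urgent and any revascularization separately.

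**Cost.** The analysis change is wording plus one interval, and Appendix B already provides for adjudicating both periods. Including index-stay events does change the endpoint: index-stay revascularizations would overlap with Aim 2, and a higher event rate widens the margin that can be excluded. The safety statement will also be more cautious.

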7.3 Tertiary Aims

To determine whether CT leads to increased test burden after the initial tests during index hospitalization

To compare the consistency of physician decision management depending on the results of the diagnostic testing (i.e. normal CT – what fraction is immediately discharged)

To determine whether hospital setting, availability of Observation Unit, CT experience of hospital and readers and reader performance are associated with primary or secondary outcomes.

Analysis of Data on Women and Minorities

We will analyze the effect of the intervention on women and minorities as outlined in the NIH guidelines. Thus, we include testing for gender-treatment and minority status-treatment interactions with the discharge rate and the angiogram rate.

8. Data Entry and Site Monitoring

8.1 Data Collection

Subject data will be collected by the research associates and paper records will be maintained at individual clinical sites. The Data Coordinating and Statistical Center (DCSC) will develop a web based electronic case report form. The de-identified study data will be entered into this electronic data capture system (EDC) and sent to the Data Coordinating and Statistical Center (DCSC) at Massachusetts General Hospital for further analysis.

